7.1 Study Intervention/Device Description

Vactosertib is an off-white solid, and a crystalline, non-hygroscopic material, with a single endothermic event at 143.5°C. Vactosertib exhibits a high aqueous solubility at low pH range which decreases with increasing pH, a behavior consistent with a weak basic molecule (TED-133). General information regarding the drug substance is provided below:

Appearance	White to off-white, crystalline powder
Thermogravimetric Analysis (TGA)	< 0.12% weight loss up to about ~130 °C
Differential Scanning Calorimetry (DSC)	Endothermic transition with onset at ~138 °C
Hygroscopicity	No weight gain was observed in the range of 25%-92% relative humidity at 25 °C; non-hygroscopic
Powder X-Ray Diffraction	Crystalline
pH (in water at 25 ± 3 °C)	Aqueous solubility: < 0.02 mg/mL; pH of a saturated solution: 7.2
pH-Solubility Profile	The solubility is higher at lower pH range (eg, 25.05 mg/mL at pH

7.2 Availability

Vactosertib is an investigational agent supplied to investigators by MedPacto Inc.

7.3 Acquisition and Accountability

Vactosertib Inventory Records– The investigator, or a responsible party designated by the investigator, will maintain a careful record of the inventory and disposition of all agents received from MedPacto Inc. on a Drug Accountability Record Form (DARF).

7.4 Formulation, Appearance, Packaging, and Labeling

For clinical studies, film-coated tablets containing 10, 20, 50, 100 and 200 mg of vactosertib are currently available. The vactosertib film-coated tablets are formulations for oral administration. They are plain, white to off-white, round, biconvex tablets containing vactosertib drug substance. The vactosertib film-coated tablets contain the following inactive ingredients: lactose monohydrate (Fastflo 316), microcrystalline cellulose(Avicel PH 102), crospovidone (Kollidon CL F), povidone Kollidon 30, magnesium stearate, and opadry white. The proposed clinical drug product vactosertib (10, 20, 50,100 and 200 film-coated tablets) is compressed from 5% w/w (10, 20mg), 10% w/w(50mg), 40%w/w(100, 200mg) drug loaded common stock wet granulation, and the same manufacturing process is used for all film-coated tablets.

7.5 Product Storage and Stability

Vactosertib tablets (10, 20, 50 and 100 mg) are packaged in tightly closed, white, opaque, HDPE bottles with a 1-g silica gel desiccant canister. The bottles are heat-induction sealed with a child-resistant cap. Based on the available laboratory stability data, vactosertib tablets (10, 20, 50, 100 and 200mg), should be stored at 15°C to 25°C (59°F to 77°F) and protected from light. Recent data indicate that 10 mg, 20 mg, and 50 mg vactosertib remain stable up to 36 months, 60 months, and 30 months, respectively, under all testing conditions with the exception of high-intensity fluorescent visible light with a minimum of 200-watt h/m² UV-A irradiation. 100 mg and 200 mg Vactosertib remain stable up to 3 months under the same testing conditions as above. Stability test for a longer

time period is underway: 50 mg, 100 mg, and 200 mg vVactosertib up to 60 months, 24 months, and 24 months, respectively.

The product should be stored in the bottle provided and used according to the instructions on the label.

7.6 Preparation

N/A

7.7 Dosing and Administration

Vactosertib tablets will be administered orally twice a day in a 5-days on, 2 days off regimen. Treatment will be administered on an outpatient basis. Reported adverse events and potential risks are described in Section 13. Appropriate dose modifications for vactosertib are described in Section 6.

7.7.1 Dose adjustment rules for Tier 1, C1D1 (D0) and interval study visits

Tier 1 - C1D1 (D0)

Overview of study visit interval:

All subjects begin treatment on C1D1 (D0) at DL1 of vactosertib (50mg BID). All subjects return one week (7 days \pm 2) after C1D1 (D0) and the vactosertib dose is adjusted according to the dose adjustment rules defined in Section 7.7.1 Table 3. The study visit interval is weekly (7 days \pm 2) any time the dose adjustment rule dictates dose escalation or a dose hold. If the dose adjustment rule dictates maintaining the current dose, then the visit interval is extended to approximately every 2 weeks. After at least two, consecutive 'Maintain' dose-adjustment decisions at the same dose level, then the next visit is extended to no later than Day 1 of the next cycle of vactosertib (approximately every 4 weeks).

Once Tier 1 has enrolled 3 patients, enrollment will be held until each patient has completed at least the first cycle of therapy before enrollment is re-opened.

Study Visit Interval Based Upon Dose Adjustment Decision:

All subjects begin treatment on C1D1 (D0) at DL1 of vactosertib (50mg BID for Tier 1). All subjects return one week (7 days \pm 2) after C1D1 (D0) and the vactosertib dose is adjusted according to the dose adjustment rules defined in Section 7.7.1 Table 3. The study visit interval is weekly (7 days \pm 2) any time the dose adjustment rule dictates dose escalation or a dose hold. If the dose adjustment rule dictates maintaining the current dose, then the visit interval is extended to approximately 2 weeks. After at least two, consecutive Maintain dose-adjustment decisions at the same dose level, then the next visit is extended to no later than Day 1 of the next cycle of vactosertib (approximately every 4 weeks).

7.7.2 Dosing Delays/Dose Modifications for vactosertib

Clinical Parameter	Escalate to Next Dose Level	Maintain Current Dose Level	Hold Dose	Restart After Dose Hold
Erythropoietic Response	Inadequate	Adequate		
Hemoglobin (HGB) absolute value, change in HGB from baseline*, and Erythrocyte transfusion	HGB ≤10 g/dL AND ≤2 g/dL increase from baseline HGB OR any Erythrocyte transfusion	HGB >10 g/dL OR >2g/dL increase from baseline HGB AND No Erythrocyte transfusion	HGB >12 g/dL	HGB<12 g/dL
Current Toxicity (CTCAE v5)	≤Grade 2	≤Grade 2 OR >Grade 2 not requiring change in treatment	>Grade 2 Requiring Change in Treatment	<Grade 2 and Requiring No New Change in Treatment
Dose hold Toxicity during Cycle	Dose Hold Not Required During Cycle	Dose Hold Not Required During Cycle		
Current Dose Dose Levels: (DL0) 50 mg daily; (DL1) 50 mg bid; (DL2) 100 mg bid; (DL3) 150 mg bid; (DL4) 200 mg bid.	< Highest Dose Level	≤ Highest Dose Level		Most Recent Dose >(DL0)
Dosing schedule, 5 days on, 2 days off				
Rule	All True	All True	Any True	All True
Next Study Visit [†]	7±2 days	1 st Maintain [§] 14±3 days 2 nd or greater Maintain D1 of next cycle	7±2 days	7±2 days

Table 3: Intrapatient Dose Adjustment Rules.

The parameters shown are used to adjust the vactosertib dose on a continuing basis. The dose is escalated to the next level if ALL criteria for escalation are met. The decision to Hold vactosertib is made if ANY hold criteria is met at any point during the cycle. Otherwise the dose level is maintained. The criteria to Escalate, Maintain or Hold a dose are non-overlapping. Dose decrements by one level will follow any HOLD. * Baseline HGB is defined as the median HGB in the 4 weeks prior to D1 of protocol treatment. † Subject will maintain a diary of adverse events between study visits. [§]Visits are weekly if there is a dose change (Escalate, Hold or Restart). Visits are bi-weekly if the decision is to Maintain the current dose. Visits are extended to every 4 weeks (D1 of each new cycle) after the second or greater, consecutive Maintain decision.

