7.9 Duration of Therapy and Criteria for Removal from Study

- 7.9.1. Tier 1 duration is 16 weeks (4 treatment cycles) and Tier 2 duration is 24 weeks (6 treatment cycles).
- 7.9.2. In the absence of treatment delays due to adverse event(s), treatment may continue for 6-10 cycles or until one of the following criteria applies:
 - 7.9.2.1. Disease progression at the MTD,
 - 7.9.2.2. Intercurrent illness that prevents further administration of treatment,
 - 7.9.2.3. Unacceptable adverse events, specifically:
 - Adverse event(s) that necessitate a dose hold for >28 days,
 - Adverse events that occur at DLO
 - 7.9.2.4. Patient decides to withdraw from the study, or
 - 7.9.2.5. General or specific changes in the patient's condition render the patient unacceptable for further treatment in the judgment of the investigator.

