8.2 Participant Discontinuation/Withdrawal from the Study

Participants are free to withdraw from participation in the study at any time upon request. An investigator may discontinue or withdraw a participant from the study for the following reasons:

- Pregnancy
- Significant study intervention non-compliance
- If any clinical adverse event (AE), laboratory abnormality, or other medical condition or situation occurs such that continued participation in the study would not be in the best interest of the participant
- Disease progression which requires discontinuation of the study intervention
- Participant lost to follow-up after several attempts to contact subject to schedule study visit.

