12.2.2 Composite response/ Toxicity measure

Responding subjects will have met *Criteria for Clinical Benefit* ([section 9.1](#)) for at least 8 weeks. This will ensure that a stable vactosertib dosing schedule can be achieved. Responding subjects will not experience dose limiting toxicity (see *Definition of Dose Limiting Toxicity*). Only subjects meeting all criteria will be considered responders.

Table 5: Composite Response & Toxicity Endpoint

Adequate Response	Meets Criteria for Clinical Benefit
Stable Response	Meets Criteria for Clinical Benefit to vactosertib for \geq 8 weeks
Tolerable	No Dose Limiting Toxicity Experienced

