Table 11: Adverse drug reaction (≥3%) from vactosertib monotherapy

AE Terms	MP-001 (n=35), n (%)	MP-VAC-105 (n=16), n (%)	MP-MDS-01 (n=9), n (%)	Total (n=60), n (%)
Headache	5 (15)	5 (32)	1 (12)	11 (19)
Fatigue	10 (29)	0 (0)	1 (12)	11 (19)
Nausea	9 (26)	1 (7)	0 (0)	10 (17)
Diarrhoea	5 (15)	1 (7)	1 (12)	7 (12)
Decreased appetite	6 (18)	0 (0)	0 (0)	6 (10)

Vomiting	5 (15)	0 (0)	0 (0)	5 (9)
Hypophosphataemia	3 (9)	0 (0)	1 (12)	4 (7)
Constipation	4 (12)	0 (0)	0 (0)	4 (7)
Dermatitis acneiform	2 (6)	0 (0)	1 (12)	3 (5)
Aspartate aminotransferase increased	3 (9)	0 (0)	0 (0)	3 (5)
Pruritus	3 (9)	0 (0)	0 (0)	3 (5)
Abdominal pain	2 (6)	0 (0)	0 (0)	2 (4)
Alanine aminotransferase increased	2 (6)	0 (0)	0 (0)	2 (4)
Amylase increased	2 (6)	0 (0)	0 (0)	2 (4)
Anaemia	2 (6)	0 (0)	0 (0)	2 (4)
Blood alkaline phosphatase increased	2 (6)	0 (0)	0 (0)	2 (4)
Dysgeusia	2 (6)	0 (0)	0 (0)	2 (4)
Dyspepsia	2 (6)	0 (0)	0 (0)	2 (4)
Lipase increased	2 (6)	0 (0)	0 (0)	2 (4)
Muscular weakness	2 (6)	0 (0)	0 (0)	2 (4)
Pyrexia	2 (6)	0 (0)	0 (0)	2 (4)
Rash maculo-papular	2 (6)	0 (0)	0 (0)	2 (4)

- Vactosertib may increase immunologic toxicities of when administered in combination with anti-cancer PD1/PD-L1 pathway inhibitors.

Dose Limiting Toxicity.

- Dose limiting toxicity is defined as any of the following: Any occurrence of death as result of adverse event regardless of attribution;
- Any non-hematologic grade ≥ 3 toxicity (CTCAEv5 criteria), except for nausea, vomiting or diarrhea lasting 3 days or less;
- Any grade 4 neutropenia (CTCAEv5 criteria) of any duration;
- Any grade ≥ 3 neutropenia that has not recovered to grade ≤ 2 within 7 days of onset;
- Any grade ≥ 3 febrile neutropenia (temperature \geq);
- Any grade ≥ 3 thrombocytopenia associated with clinically significant bleeding; or requiring platelet transfusion.

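### Table 3 is not linked to the DLT definition, so a patient with a new DLT that led to no hold can be escalated, possibly within the same cycle

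*Combined protocol and SAP*

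**What the plan says.** **Dose rule (section 7.7.2, Table 3).** Escalation requires all of the following: inadequate erythropoietic response, current toxicity of Grade 2 or less, a dose below the highest level, and "Dose Hold Not Required During Cycle". Hold applies to hemoglobin above 12 g/dL, or to toxicity above Grade 2 that requires a change in treatment. The Maintain column's toxicity entry reads "≤Grade 2 OR >Grade 2 not requiring change in treatment". The footnote sets the default: "The decision to Hold vactosertib is made if ANY hold criteria is met at any point during the cycle. Otherwise the dose level is maintained". Any hold is followed by a one-level reduction. Neither Table 3 nor section 6.3.3 refers to DLT, and the phrase about a change in treatment is not defined.

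**DLT definition (section 13.1.1, Dose Limiting Toxicity).** The list includes "Any non-hematologic grade ≥ 3 toxicity (CTCAEv5 criteria), except for nausea, vomiting or diarrhea lasting 3 days or less" and grade 4 neutropenia of any duration. Neither entry depends on whether treatment is changed.

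**Where DLT is used.** It enters the stopping rules (8.1), the unscheduled interim analysis (12.5), the composite endpoint (12.2.2), the Tier 2 starting dose (6.3.6.3, 12.6.3) and continuation after planned therapy (6.3.7). None of these tells the clinician how to dose the patient who had the DLT.

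**Patient-level safeguards.** Section 7.9.2 removes a patient for a hold longer than 28 days or an adverse event at DL0. It also covers changes that "render the patient unacceptable for further treatment in the judgment of the investigator". Section 8.2 permits withdrawal when "continued participation in the study would not be in the best interest of the participant".

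**The concern.** The same protocol classifies toxicity in two ways. Section 13.1.1 goes by type and grade. Table 3 goes by grade and a judgment about changing treatment. An event can be a DLT under the first and a Maintain under the second. The in-cycle lock on escalation is triggered by holds, not DLTs, so such an event leaves no mark on the next dosing decision.

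What is at stake is mainly the safety of the individual patient. Section 1 makes the Table 3 algorithm the means of establishing a safe and tolerable dose, and section 6.3.6 carries the same rules into Tier 2, so the gap is open for all 37 planned patients. Under section 12.2.2, "Responding subjects will not experience dose limiting toxicity", so a higher dose after a DLT cannot make that patient a composite responder, although it could still bring clinical benefit.

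**Working it through.** The plan states no figure on this point. The check applies the Table 3 logic to cases and then does visit-calendar arithmetic.

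**1. Decision logic.** Hold if any hold criterion is true; otherwise Escalate if all escalate criteria are true; otherwise Maintain, by the footnote's default. Illustrative patient: DL1, hemoglobin 8.5 g/dL, transfused (inadequate response), no earlier hold in the cycle.

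| State at the visit | Table 3 decision |
|---|---|
| New grade 3 non-hematologic DLT, change required | Hold |
| New grade 3 non-hematologic DLT, no change required | Maintain |
| New grade 4 neutropenia, no change required | Maintain |
| Next visit, toxicity still grade 3, no change required | Maintain |
| Next visit, toxicity Grade 2 or less, no hold in the cycle | Escalate |

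The last row also applies to a DLT that began and settled between two visits without a hold; that route needs no Maintain step.

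**2. Timing.** Inputs: 28-day cycle (section 1); first follow-up at 7 ± 2 days (7.7.1); return after a first Maintain at 14 ± 3 days (Table 3, 6.3.3.2) or 14 ± 4 days (6.3.2). D0 is Day 1 of the cycle, so the next cycle begins at D28.

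- Maintain at D7, nominal: 7 + 14 = D21.
- With ± 3 days: earliest 7 − 2 + 14 − 3 = D16; latest 7 + 2 + 14 + 3 = D26.
- With ± 4 days: earliest 7 − 2 + 14 − 4 = D15; latest 7 + 2 + 14 + 4 = D27.

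All of these fall before D28. A first Maintain on Day 1 of a later cycle returns at D14, also in the same cycle. A first Maintain at D14 or D21 nominally returns at D28, when a new cycle starts.

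**3. Exposure in the D7 example.** Dosing is 5 days on, 2 off. From D7 to D20 the dosing days are D7–D11 and D14–D18, so 5 + 5 = 10 further days at the dose on which the DLT occurred. Daily dose then rises from 2 × 50 = 100 mg (DL1) to 2 × 100 = 200 mg (DL2), a ratio of 2.0. Later steps are 300/200 = 1.5 and 400/300 = 1.33.

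**4. Delay if escalation is barred until the next cycle.** In the example, 28 − 21 = 7 days, out of 16 × 7 = 112 days in Tier 1. If the DLT started and settled in the first week, 28 − 7 = 21 days, the nominal maximum.

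**The case against.** **Judgment is built into the rule.** The route opens only after the investigator decides that no change in treatment is needed. The opposite decision brings a hold, a one-level reduction and a bar on escalation in that cycle. The non-hematologic DLT entry has no attribution condition, so it can capture events unrelated to the drug; tying dose to clinical judgment is defensible. If a change in treatment includes supportive care, DLTs such as thrombocytopenia needing platelet transfusion would fall under Hold. This stands as a limit on how often the gap would be reached. It does not close it, because the phrase is undefined and the lock ignores DLTs that led to no hold.

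**The carve-out has a purpose.** Section 13.1.1 expects some patients to enter with pre-existing grade 3 or 4 toxicities. That probably explains the Maintain wording, but the wording is not limited to them.

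**Rarity.** Section 13.1.1 expects grade 3 or 4 drug-related toxicity to be rare, and several conditions must coincide. Against that, Table 7 reports grade 3 or 4 events in 22 of 60 patients on monotherapy, including laboratory findings (hyponatraemia 2, hypophosphataemia 1, raised ALT 1, raised AST 1) that could be judged to need no change. No rate for this route can be derived.

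**Two stronger readings are not supported.** A reader might infer that escalating after a DLT cannot contribute to any go/no-go decision. That is true of Table 5 only. The Clinical Benefit criteria and the splenic and erythropoietic rules carry no DLT exclusion for the individual patient, and they feed the Tier 2 decision (10.1), DSMB convening (8.1.1), the Tier 2 starting dose (6.3.6.3, 12.6.3) and the randomized-study criterion (12.4.2). A reader might also infer that the stopping rules never touch an individual's dose. Section 8.1.1 suspends accrual to a dose level and those above it after more than two DLTs at that level. Since everyone in Tier 1 starts at DL1, that could in effect restrict escalation to higher levels, but only after several patients are affected.

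**Conclusion.** The concern holds as a gap in the written rule. A new DLT judged to need no change in treatment does not block escalation, and neither does one that settles between visits without a hold. Escalation can follow in the same cycle when the Maintain decision falls early in it: D16 to D26 for a D7 decision under Table 3's windows, with a doubled daily dose from DL1.

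This rests on reading Table 3 literally, on toxicity returning to Grade 2 or less, on inadequate erythropoietic response and on a dose below DL4. Frequency is unknown and probably low. Investigator judgment is a real safeguard but the only one at patient level. The documents do not show that Table 3 escalates after every DLT, or that every DLT ought to force a hold. This is a cheap improvement to patient safety; it does not affect the sample size or the two-stage design.

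**What to change.** Add one line to the Escalate column of Table 3, parallel to the existing hold lock: no new DLT (section 13) during this cycle. State that a grade 3 or 4 condition recorded at baseline that has not worsened is not a new DLT. Section 13.4 already treats conditions present at screening as baseline unless they deteriorate, so a cross-reference suffices. The Maintain carve-out then keeps its likely purpose.

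This bar ends on Day 1 of the next cycle. A DLT that begins at D22 and settles by D28 could still be followed by escalation at D28. The sponsor could extend the bar past that day to cover late-cycle events. That extension, and any forced hold or reduction after a DLT, is a design choice.

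Cost: one table line and one sentence. Some patients escalate later, by 7 days in the example and at most 21 on the nominal calendar. The change adds no holds, dose reductions or removals.

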This is a two-tiered single arm Phase 2 trial of vactosertib (TEW-7197) for the treatment of anemia in Ph-neg MPNs. Both tiers use a rule-based, accelerated dose escalation scheme to efficiently assess the potential of vactosertib to safely and effectively treat anemic patients with Ph-neg MPNs. The first tier of this trial (Tier 1) is an intra-patient dose finding study in 12 patients that uses a low starting dose of vactosertib for all patients. Treatment dose is escalated according to prospectively-defined rules, and a toxicity and treatment effect algorithm (*Table 3 in section 7*) during the period of 16 weeks (4 treatment cycles). If pre-established efficacy and safety endpoints are met (*section 12.1*), then Tier 1 of the study will be followed by a Tier 2 expansion study with an additional 25 patients for a period of 24 weeks (6 treatment cycles).

Study Duration:

24 months (4 months for tier 1, 6 months for tier 2, and follow-up after intervention (2 months for patients who come off study and 12 months for patients completing study).

Participant Duration: Approximately 18 months

Study Agent: Vactosertib

Intervention Description:

Vactosertib is given oral twice a day for 5 days followed by 2 days off. The starting DL is 50mg BID (*see Table 2 in section 6 for DLs*). A cycle is defined as 4 weeks of treatment. **Primary Objective:**

- To establish a safe and tolerable dose and schedule of vactosertib in Ph-neg MPNs as determined by the study dose escalation algorithm (*Table 3 in section 7*).
- To preliminarily assess efficacy of vactosertib in treating anemic patients with Ph-neg MPNs as reported by symptomatic, splenic and/or erythropoietic response (*section 9.1*).
- To determine the safety and tolerability of vactosertib administered alone or in combination with cytoreductive therapies for MPN (approved and standard of care).

Secondary Objectives:

- To evaluate on target molecular activity of vactosertib in anemic patients with Ph-neg MPNs as determined by the following parameters:
 - Molecular response, measured by change in blood (and/or marrow) variant allelic frequency (VAF) of MPN driver mutations (JAK2, CALR or MPL).
 - Histologic response, measured by change in bone marrow biopsy cellularity and fibrosis grade.
 - SMAD2/3 phosphorylation measured by flow cytometry of peripheral blood and/or bone marrow hematopoietic cells and/or by immunohistochemical staining of bone marrow biopsy sections.

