- To identify common toxicities of vactosertib in patients with Ph-neg MPNs.

Exploratory Objectives:

To assess the stem cell directed effect of vactosertib by quantifying the VAF of MPN driver mutations in stem, progenitor and mature cell populations isolated from PB or BM samples before and after treatment with vactosertib.

Endpoints:

Primary Endpoints: (Safety and Efficacy)

- Tier 1 (Safety endpoints):
 - Define the safest, minimally effective starting DL for Tier 2 ([section 5.3.5.1](#)).
 - Identify DLTs and, possibly the MTD of vactosertib in patients with MPN
- Tier 2 Efficacy endpoints ([section 9.1](#)):
 - Erythropoietic response as defined by the IWG-MRT criteria
 - Clinical response in symptoms as defined by IWG criteria.
 - Splenic response as defined by IWG criteria.^{2,3}
- Tier 2 Safety endpoints: Identify DLT and, possibly MTD

Secondary Endpoints:

- Histologic response defined by any reduction in grade of bone marrow fibrosis by histopathologic assessment at 16 weeks.
- Molecular response defined by a decrease in VAF of MPN-driver mutations (eg. JAK2, CALR, and MPL allelic ratio) in blood and/or bone marrow cells.
- Pharmacodynamic Response defined as any of the following:
 - Reduced immunohistochemical staining for SMAD2/3 phosphorylation in bone marrow biopsy sections (*See Figure 1*).
 - Reduced mean fluorescence intensity (MFI) of SMAD2/3 phosphorylation staining in peripheral blood and/or bone marrow HSPCs or mature progeny as assessed by flow cytometry (*See Figure 2*).
- The incidence of hematologic toxicities, infections, disease progression, thrombosis events, and the probability of overall and progression free survival, will be monitored.

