3.1 Overall Design

- This is a two-tiered single arm phase 2 trial of vactosertib. Both tiers use a rule-based, accelerated dose titration scheme to efficiently assess the potential of vactosertib to safely and effectively treat anemic patients with Ph-neg MPNs. The two-tier design of this phase II study serves to limit exposure of subjects to vactosertib if we observe unexpected toxicity in the treatment of MPN patients in tier 1 before proceeding to the larger/ longer tier 2 portion of the study. The rule-based accelerated dose titration allows quick identification of the minimally effective dose range and therefore approximating “real world” clinical practice because it allows individualized dose adjustments.

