6.3.2.3. Dose Adjustment Testing and Procedures (*section 6.3.2.2*)

6.3.2.4. If Day 1 of Cycle,

- Pill Counts to assess compliance (subjects return all vials at visit for pill counts).
- Dispense study drug (vactosertib 50 mg tabs) for one cycle from research pharmacy and deliver to subject during clinic visit.
- Research blood sample (20mL) will be collected one hour after vactosertib dose (also collected on C1D8).

6.3.3. **Dose Adjustment Decision** ([see Table 3 section 7](#))

6.3.3.1. **Escalate** to next dose level

- Subject will receive one dose of vactosertib at escalated dose level under supervision of treating physician or research study nurse.
- Research blood sample (20mL) will be collected approximately 1hr after escalated dose taken.
- If dose is at maximum level (DL4), and patient has at least stable disease, then patient can remain on study at maximum level (DL4).
- If dose is at maximum level (DL4), and patient has progressive disease, then patient will be removed from study.
- Subject will return for Follow-up Testing and Procedures in 7 (\pm 2) days from start of new dose level.

6.3.3.2. **Maintain** current dose level

6.3.3.2.1. **New Maintain Decision:**

- Subject will return for Follow-up Testing and Procedures in 14 (\pm 3) days.

6.3.3.2.2. **Ongoing Maintain Decision:**

- After at least two, consecutive Maintain dose-adjustment decision at the same dose level, subject will return for Follow-up Testing and Procedures no later than Day 1 of the next cycle of vactosertib.

6.3.3.3. **Hold** vactosertib

- If last dose received is at minimum dose level (DL0), patient will be removed from study. Otherwise:

6.3.3.3.1. **New Hold Decision**

- Subject will return for Follow-up Testing and Procedures in 7 (\pm 2) days.

6.3.3.3.2. **Ongoing Hold Decision**

- If dose is held > 28 days, subject will be removed from study.
- If dose is held < 28 days, subject will return for Follow-up Testing and Procedures in 7 (\pm 2) days

6.3.3.4. **Restart** vactosertib

- Vactosertib dose will be reduced to one dose level lower than the last dose level received.
- If last dose received was at minimum dose level (DL0), patient should have already been removed from study.
- Subject will return for Follow-up Testing and Procedures in 7 (\pm 2) days from start of new dose level.
- Subject will receive one dose of vactosertib at restarted dose level under supervision of treating physician or research study nurse.

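### Table 3 has no memory of a patient's own DLT: once the cycle of the hold is over, a recovered but still anaemic patient must be escalated back to the level that caused it

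*Combined protocol and SAP*

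**What the plan says.** Table 3 governs dosing in both tiers (6.3.6.4). To escalate, all of its criteria must be true:

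- inadequate erythropoietic response: hemoglobin at or below 10 g/dL with a rise of no more than 2 g/dL, or any red-cell transfusion;
- current toxicity of Grade 2 or lower;
- "Dose Hold Not Required During Cycle";
- a current dose below the highest level.

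The legend makes this an instruction: "The dose is escalated to the next level if ALL criteria for escalation are met". If neither Escalate nor Hold applies, "Otherwise the dose level is maintained".

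A toxicity hold needs an event above Grade 2 that requires a change in treatment. Restart needs recovery to below Grade 2, and under 6.3.3.4 "Vactosertib dose will be reduced to one dose level lower than the last dose level received". Neither place says whether the reduction lasts.

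Section 13.1.1 includes among the DLTs "Any non-hematologic grade ≥ 3 toxicity (CTCAEv5 criteria), except for nausea, vomiting or diarrhea lasting 3 days or less". The Protocol Summary states "A cycle is defined as 4 weeks of treatment", without saying whether the cycle runs on during a hold.

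**The concern.** The DLT definition and the hold criterion largely coincide for non-haematologic events. Apart from short nausea, vomiting or diarrhea, every such event that triggers a toxicity hold is a DLT. The dosing rule nevertheless forgets the event when the bar tied to the cycle lifts.

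Patients enter the trial anaemic, so the efficacy trigger for escalation is the default state of anyone who has not responded. Such a patient, once recovered, meets every Escalate criterion and is sent back to the dose that produced the DLT. The toxicity threshold for that step (Grade 2 or lower) is looser than the threshold for restarting at the reduced dose (below Grade 2).

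Elsewhere the protocol does treat a DLT as lasting information about the patient. It rules out a composite response (Table 5), and it rules out continuing treatment on stable disease alone (6.3.7). Only the dosing rule drops it. At stake is avoidable re-exposure of individual patients, which the study-level rules would not register as a new patient with a DLT.

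**Working it through.** The plan gives no figure to reproduce here, so the check is to walk Table 3 visit by visit.

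**Inputs.** Visits are 7 days after Escalate, Hold or Restart, 14 days after a first Maintain, and on Day 1 of every later cycle (6.3.2, Table 3). A cycle is 4 weeks (Protocol Summary). Holds may last up to 28 days (6.3.3.3). Hold lengths of 7, 14 and 21 days are assumptions.

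**Example.** DLT at DL2, hold on cycle day 14, 7-day recovery, calendar cycles.

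1. Day 14: hold.
2. Day 21: restart at DL1.
3. Day 28 is Day 1 of the next cycle. Hemoglobin is still inadequate, toxicity is Grade 2 or lower, no hold has been required in this cycle, and DL1 is below DL4. All criteria are true, so the dose goes to DL2.
4. Interval from hold to return: 28 − 14 = 14 days.

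**General form.** With hold length L, days to return = the larger of (L + 7) and the days until the first decision visit after the bar lifts. The smallest nominal value is 7 + 7 = 14. If both visits fall at the early edge of their ±2-day windows it is 5 + 5 = 10.

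**Days from hold to return, by reading of the bar:**

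| Reading | Hold (days) | Held on cycle day 0 | 7 | 14 | 21 |
|---|---|---|---|---|---|
| Bar = calendar cycle of the hold | 7 | 28 | 21 | 14 | 14 |
| | 14 | 28 | 21 | 21 | 21 |
| | 21 | 28 | 28 | 28 | 28 |
| Bar also covers the cycle of restart | 7 | 28 | 21 | 14 | 35 |
| | 14 | 28 | 21 | 42 | 35 |
| | 21 | 28 | 49 | 42 | 35 |
| Cycle clock pauses during the hold | 7 | 35 | 28 | 21 | 14 |
| | 14 | 42 | 35 | 28 | 21 |
| | 21 | 49 | 42 | 35 | 28 |
| Day 1 visit looks back at the cycle just completed | 7 | 56 | 49 | 28 | 14 |

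The last row, for a hold on day 0: restart on day 7; Maintain on day 14; Day 1 visit on day 28 still barred, so a second Maintain; next visit on day 56, escalate. No reading prevents the return; each only delays it.

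**Size of the step on return** (daily dose): DL0 to DL1, 50 to 100 mg, +100%; DL1 to DL2, 100 to 200 mg, +100%; DL2 to DL3, 200 to 300 mg, +50%; DL3 to DL4, 300 to 400 mg, 100/300 = +33%.

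**Other text that might impose a ceiling:**

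- 6.3.3.3 and 7.9.2.3 remove patients for holds over 28 days or events at DL0. A DLT above DL0 that recovers in time is not covered.
- 7.9.2.5 and 8.2 let the investigator withdraw a patient. This is discretion to stop, not a dose limit for someone who stays.
- 8.1.1 suspends accrual to a dose level after more than two patients have a DLT there; 12.5 does so after more than three. One patient's DLT triggers neither.
- 8.1.1, 8.1.2 and 12.5 count patients with a DLT. A second, non-fatal DLT in the same patient at the same level leaves every count unchanged.

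Parts of the text in section 3.3 and following 2.2.3 were not available to read. Nothing in the rest caps a patient below the level of that patient's own DLT.

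**The case against.** The strongest reply is that re-challenge after recovery is coherent in a design whose aim is "individualized dose adjustments" (3.1). Table 3 blocks escalation while the bar lasts. Restart requires recovery and a lower dose, a visit follows at that lower dose, and any return begins with a supervised dose and a visit 7 days later. All of this is true and limits the harm. It does not make re-challenge a stated choice. The text neither says that return to a DLT level is intended nor sets conditions for it.

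In Tier 1 everyone starts at DL1, so suspending accrual to higher levels may well mean stopping escalation into them, which would cap patients already on study. That reading is reasonable, but it still needs several patients with a DLT at one level.

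The DLT definition for non-haematologic events has no attribution requirement, and 13.1.1 expects some patients to arrive with Grade 3 or 4 toxicity. A DLT may therefore say little about the dose. This stands, and the remedy must allow for it.

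Stronger inferences are tempting but unsupported. A reader might infer that the protocol contradicts itself. It does not, because the reduction is nowhere called permanent; this is a gap. A reader might also infer that return always comes within 28 days. That holds only on some readings and hold lengths. Finally, a reader might put a number on the patients affected. That needs the share of DLT patients who are held, recover in time and stay anaemic, and no document gives it.

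**Conclusion.** The point holds as a gap in the dosing rule. Followed as written, Table 3 requires re-escalation to the level of a patient's own DLT when four things are true: the DLT led to a hold above DL0, the patient recovered within 28 days, the erythropoietic response is still inadequate, and current toxicity is Grade 2 or lower.

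The mechanism and the nominal minimum of about 14 days are firm. The upper end is not: it is 28 days with calendar cycles and holds of up to 21 days, and up to about 56 days on other readings. Frequency cannot be estimated.

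The finding does not show that the trial lacks safeguards, since the investigator can withdraw a patient at any time. Nor does it show that the efficacy decision in 12.1 is distorted. It is a cheap improvement to patient protection.

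**What to change.** Extend the Escalate cell that now reads "Dose Hold Not Required During Cycle" with: *and the next-higher level is not at or above a level at which this patient had a DLT that required a dose hold, unless the event is clearly shown to be unrelated to vactosertib by the standard of 13.1.2.* The patient then stays at the reduced level through the existing default, "Otherwise the dose level is maintained". Holds for hemoglobin above 12 g/dL, toxicity holds that are not DLTs, and DLTs that needed no hold keep the present rule. If the sponsor does intend re-challenge, the alternative is to say so and state its conditions.

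The cost is one amended cell. A few patients with a DLT would stay at a lower dose, and fewer would reach the top levels. Some of them might miss a response that counts outside the composite: the Summary lists "Erythropoietic response as defined by the IWG-MRT criteria" as a Tier 2 primary endpoint, and 12.4.2 counts splenic and erythropoietic responders. Such a response would also matter for the Tier 1 decision if that were read, under 8.1.1 or 10.1, as clinical benefit alone. The gates in 12.1 (1 or more of 12, 4 or more of 37) do not change, because Table 5 already excludes any patient with a DLT from being a composite responder.
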